2.2 Informed consent of human subjects

The investigator must assure the study monitor that the informed consent form for a subject:

- 2.2.1 Meets ICH guidelines as defined in ICH E6, Section 4.8, Informed Consent of Trial subjects
- 2.2.2 Has been approved by the IRB or IEC, including (when required) information to be given to the subject about the trial in which he or she is enrolled
- 2.2.3 Includes the basic elements and any additional elements of informed consent that are appropriate
- 2.2.4 Has been signed by both the subject (or the subject's legally acceptable representative), the investigator, and a witness, and a copy has been given to the subject
- 2.2.5 Is provided, if necessary, to the subject in the "short form" informed consent form (presented orally to the subject or the subject's legally acceptable representative, with a witness listening) with written information as an alternative
- 2.2.6 Allows for assent to be obtained for minor children as required by the IRB or IEC

2.3 Storage and dispensing of product supplies

The investigator (or the investigator's pharmacist) must assure the study monitor that:

- 2.3.1 Adequate and accurate written records show receipt and disposition of all product supplies, including dates, serial or lot numbers, quantities received, and each quantity dispensed, administered, or used, with identification of each subject.
- 2.3.2 Purpose and reasons are given in written records for product disposal (e.g., the amount contaminated, broken, or lost) and the quantity that was returned to the sponsor.

2.4 Case report forms

The investigator must assure the study monitor that:

- 2.4.1 The completed eCRF accurately reflects the hospital records for each subject.
- 2.4.2 The eCRFs and hospital records will be accessible to the study monitor during on-site visits.

2.5 Files and records

The investigator must ensure the quality, integrity, and content of his or her files, which will be subject to audit by the study monitor and the appropriate regulatory authority inspectors. The files must contain, as minimum the following:

- Investigator's Brochure
- Investigator's obligations, including the following:
 - 1. 21 Code of Federal Regulations (CFR) Part 312.50, General Responsibilities of Sponsors
 - 2. 21 CFR Part 312.60, General Responsibilities of Investigators
 - 3. 21 CFR Part 50, Protection of Human Subjects
 - 4. 21 CFR Part 56, Institutional Review Boards
 - ICH, E6, Guideline for Good Clinical Practice
- IRB or IEC-approved protocol and protocol amendments
- Blank eCRFs (and amendments to eCRF)
- Study procedures manual and amended pages
- Statement of investigator forms (copy of signed Form FDA 1572 and a copy of each revised form if required by the regulatory agency) as well as current curricula vitae and bibliography for each investigator and subinvestigator

- IRB or IEC document, including the following:
 - 5. IRB or IEC charter membership and qualifications of each member
 - 6. IRB or IEC letter of approval of protocol and amendments
 - 7. IRB or IEC letter of approval of informed consent form and amendments
 - 8. Investigator's annual report to the IRB or IEC
 - 9. IRB or IEC annual re-approval of protocol
 - 10. Reports to IRB or IEC of deaths and serious adverse events (SAEs)
 - 11. Notification to IRB of study completion and investigator's final report
 - 12. IRB approval of advertisements for subject recruitment (if applicable)
 - All additional correspondence with the IRB/IEC
- IRB/IEC approved informed consent document (all versions) and information to be supplied to the subject
- Study staff signature log
- Subject accountability records, including the following:
 - 13. Subject screening log
 - 14. Medical exceptions log
 - 15. Site status report
 - 16. Subject identification code list
 - 17. Original signed informed consent form
 - 18. A note stating the location of the eCRFs and data clarification requests
 - Copies of completed eCRF transmittal logs
- Investigation product records, including the following:
 - 19. Receipt, date and quantity, and batch or lot number
 - 20. Disposition dates and quantity administered to each subject
 - 21. Inventory records
 - All correspondence related to the investigational product

- SAE/safety reports
 - Copies of signed SAE reports
 - All SAE correspondence, including MedWatch and Form FDA 3500A
- Biological sample inventory forms and correspondence with the analytical laboratory
- Monitoring activities
 - 22. Monitoring log (should include all visits [i.e., site initiation, periodic, and termination visits])
 - 23. Telephone contact reports
 - 24. Site initiation visit reports
- General Correspondence
 - 25. All correspondence between the study monitor, sponsor, and the site
 - 26. All correspondence between site staff about the protocol

Documents and records must be retained by the investigator for at least 2 years after the last approval of a marketing application in an ICH region and until there are no pending or contemplated marketing applications in an ICH region or for at least 2 years after the formal discontinuation of clinical development of the investigational product.

Clinical Protocol

APPENDIX D PARTIAL MAYO SCORE QUESTIONNAIRE

HTD1801.PCT003 Study Partial Mayo Score Questionnaire

Subject #:	Subject Initials	:		
Date of visit:				
Visit Name: Sci	reening Baseline	Week 6	Week 12	Week 18
Patients will fill out the first two questions, and the physician will fill out the last question.				
Patients: please select an option below based on stool frequency in the past 3 days.				
1. Stool Frequency □ Normal number of stools for patient □ 1 to 2 stools per day more than normal □ 3 to 4 stools more than normal □ ≥ 5 stools more than normal □ 3 to 4 stools more than normal				
Patients: please select an option below based on rectal bleeding in the past 3 days.				
2. Rectal Bleeding No blood seen Streaks of blood with stool less than half of the time Obvious blood with stool most of the time Blood alone passes			= 0 = 1 = 2 = 3	
Physicians: Please select an option below:				
3. Physician's Global Assessment:				
□ M □ M	ormal lild disease loderate disease evere disease		= 0 = 1 = 2 = 3	
Site staff: To calculate the total score, either enter the responses onto the Partial Mayo Score EDC page of the appropriate visit OR manually calculate the sum using the response values noted above and record total score on the visit worksheet.				
Study coordinat	or or PI initials:		Date	
HTD1801 PCT003 Partial Mayo Score Questionnaire v1 0			IRB appr	oved date:

1. INTRODUCTION

This document describes the statistical methods and data presentations to be used in the summary and analysis of data from Protocol HTD1801.PCT003. Background information is provided for the overall study design and objectives. The reader is referred to the study protocol and case report forms (CRFs) for details of study conduct and data collection.

1.1. STUDY OVERVIEW

Protocol HTD1801.PCT003 is a Phase 2, randomized, double-blind study which consists of a placebo- and dose-controlled parallel group period, a dose-controlled extension period, and a placebo-controlled randomized withdrawal period with the intent of comparing multiple doses of investigational product (HTD1801) to placebo. Approximately 60 patients with Primary Sclerosing Cholangitis (PSC) will be enrolled as subjects. Upon confirmation of eligibility, subjects will be randomized in Period 1 in a 1:1:1 ratio, stratified by inflammatory bowel disease (IBD) diagnosis and ursodiol (UDCA) status, to one of the following treatment arms:

- **Treatment Arm 1:** HTD1801 500 mg twice daily (BID)
- **Treatment Arm 2:** HTD1801 1000 mg BID
- **Treatment Arm 3:** Placebo BID.

Subjects will receive the treatment to which they are randomly assigned for 6 weeks during the first period.

In response to the COVID-19 pandemic, enrollment into the study was prematurely stopped on 25th March 2020. This impacted 3 subjects who had been randomized but had not yet initiated dosing. There may be additional restrictions associated with COVID-19 that may impact sites' ability to schedule subjects for in-clinic visits and thus, complete all protocol-required assessments. These will be noted as protocol deviations related to COVID-19 should they occur. These measures were put into place following the issuance of the FDA Guidance on Conduct of Clinical Trials of Medical Products during COVID-19 Pandemic (March 2020 and April 2020).

See [Section 3.2](#) for additional details on Period 1 randomization.

Following the completion of the first period, subjects are eligible to enroll in Period 2 which is a 6-week extension period. During this period, subjects who were previously randomized to 500 mg or 1000 mg BID in Period 1 will continue to receive the same dose. Subjects who were previously randomized to placebo will be randomized in a 1:1 ratio to receive 6 weeks of either 500 mg or 1000 mg BID. This period will continue to be double-blind.

Following the completion of Period 2, the 6-week treatment extension period, all subjects will be randomized in a 1:1 ratio to either continue on the active treatment they received in the second period or be assigned to placebo.

An independent Data and Safety Monitoring Board (DSMB) will provide additional safety oversight.

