8.2.3 Efficacy Analysis

The mITT population will be used for the analysis of all efficacy endpoints. No alpha adjustments for multiplicity will be made for the analysis of efficacy endpoints for this proof of concept study.

The primary efficacy variable is the change in ALP from Baseline to Week 6 in the double-blind parallel group period. Changes in ALP from Baseline will be summarized by treatment group and visit using descriptive statistics. A mixed model repeated measures (MMRM) will be fit to the data and the model will include fixed factors for treatment, randomization strata of IBD diagnosis, visit and treatment by visit interaction, and Baseline value as a covariate. An unstructured covariance matrix will be used to model the repeated assessment over time. Denominator degrees of freedom will be adjusted using Kenward-Roger's method. Sensitivity analyses will be described in the statistical analysis plan (SAP). Treatment comparisons will be made at each visit,

with the primary comparison at Week 6. No imputation of missing data is necessary for the MMRM analysis of the primary endpoint. A similar MMRM analysis will be performed for the randomized withdrawal period. Analysis for the randomized withdrawal period will be conducted for all subjects and separately for responders based on pre-specified responder criteria. For the dose-controlled treatment period, a one sample t-test will be used to evaluate the change in ALP from Week 6 to Week 12 for the subjects who were previously randomized to placebo during the first period.

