4.1. MODIFIED INTENT-TO-TREAT POPULATION

The mITT population will consist of all randomized subjects who receive at least one dose of study drug and who have at least one post-dose efficacy assessment. Subjects in this population will be

analyzed according to the treatment group to which they were randomized. This population will be used for analyses of efficacy.

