5.2.5. Secondary Efficacy Analysis

All secondary endpoints will be summarized descriptively by treatment group and visit as defined for each period. Continuous endpoints will present baseline and actual value summaries and change from baseline (Period 1), Week 6 (Period 2), or Week 12 (Period 3) as appropriate. Proportions will be presented with denominators based on the number of subjects randomized to each treatment group.

The mean ALP values will additionally be represented graphically via a line chart for Period 2 and Period 3, with one page for each treatment group, with a line for each subject within the group charted individually, and with one line for the overall group. Period 2 will graph values for all scheduled visits from Baseline through Week 12 and Period 3 will graph values for all scheduled visits from Baseline through Week 18.

Absolute change in GGT from Baseline to Week 6 will be tested using a mixed model with repeated measures (MMRM) analogous to the primary endpoint ([Section 5.2.2](#)). This model will include fixed effects for treatment, IBD diagnosis, UDCA status, visit and treatment by visit interaction, with Baseline GGT value as a covariate. An unstructured covariance matrix will be used to model the repeated assessments over time. Denominator degrees of freedom will be adjusted using Kenward-Roger's method. Least Square (LS) Means and corresponding standard errors and 95% confidence intervals resulting from the model described will be presented at each visit. Differences in LS Means and corresponding two-sided 95% confidence intervals will be calculated at each visit comparing each active arm to placebo as well as comparing the HTD1801 1000 mg BID treatment group to the HTD1801 500 mg BID treatment group. The primary comparison of these treatment groups will be at Week 6.

Absolute change in GGT from Baseline to Week 6 will also be summarized by the subgroups as detailed in [Section 5.2.3](#).

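### SAP 5.2.5 divides responder proportions by the number randomised, while SAP 4.1 assigns efficacy to the mITT population; three undosed subjects make the two rules give different Period 1 ALP responder rates

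*SAP*

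**What the plan says.** Four parts of the SAP and one of the protocol bear on this.

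- **SAP 1.1:** "enrollment into the study was prematurely stopped on 25th March 2020", and "This impacted 3 subjects who had been randomized but had not yet initiated dosing".
- **SAP 4.1:** the mITT population is "all randomized subjects who receive at least one dose of study drug and who have at least one post-dose efficacy assessment", grouped as randomised. It adds: "This population will be used for analyses of efficacy".
- **Protocol 8.2.3:** "The mITT population will be used for the analysis of all efficacy endpoints".
- **SAP 5.2.5:** "Proportions will be presented with denominators based on the number of subjects randomized to each treatment group".
- **SAP 8:** group headers carry the sample size of the analysis population named for the table. Percentages in frequency tables use the total count shown in that module, and missing observations are noted.

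The endpoints concerned are the three ALP responder proportions in SAP 5.2.4: ALP below 1.5 x ULN, a fall of at least 50%, and normalisation, each at the end of each period. SAP 7 makes all three descriptive with no testing. It does not mention a change of denominator.

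**The concern.** The documents give three denominators for the same percentage: randomised (SAP 5.2.5), mITT (SAP 4.1 and protocol 8.2.3), and the table total (SAP 8). If everyone randomised had been dosed and assessed, the first two would coincide. SAP 1.1 shows that they do not.

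A subject with no dose has no post-dose ALP and cannot be counted as a responder. Kept in the denominator, that subject has the same effect as a non-responder, for a reason unrelated to the drug. The responder table would then rest on a different set of subjects from the ALP change table beside it. Two programmers working from the same SAP could also produce different percentages.

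The ALP responder results will be read closely in a proof-of-concept trial of about 60 subjects, even though they are untested.

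**Working it through.** **Inputs from the documents**
- Randomised without dosing begun: 3 (SAP 1.1). Their arms are not given.
- Allocation 1:1:1 (SAP 1.1).
- Total randomised: SAP 3.2 gives 42 + 17 = 59 and does not say whether the three are among them. The revised target in SAP 3.1 is 63. Per arm this is 59/3 = 19.7 to 63/3 = 21.

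**Assumptions**
- 20 randomised per arm, with 19 to 21 as the range.
- The three subjects were never dosed later, and every dosed subject is in the mITT population.
- A 40% responder rate among dosed subjects, for illustration. Neither document gives an expected rate.

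**The plan's own figures.** The SAP states no responder rate to reproduce. Its sample sizes do reproduce with SD 200 and two-sided alpha 0.05: t-test power is 79.9% for a difference of 147 with 30 per group, and 81.2% for 180 with 21 per group. The point does not depend on them.

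**Formula.** Let N be the number randomised to an arm, u the number of those undosed, and r the responders.
- mITT rate = r / (N - u)
- Rate under SAP 5.2.5 = r / N = mITT rate x (N - u) / N

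**With N = 20 and an mITT rate of 40%**

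| u | Factor (N - u)/N | Rate shown |
|---|---|---|
| 0 | 20/20 = 1.00 | 40% |
| 1 | 19/20 = 0.95 | 38% |
| 2 | 18/20 = 0.90 | 36% |
| 3 | 17/20 = 0.85 | 34% |

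**With whole subjects**
- 10 responders, 1 undosed: 10/19 = 52.6% (mITT) against 10/20 = 50.0% (randomised).
- 8 responders, 3 undosed: 8/17 = 47.1% against 8/20 = 40.0%.

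**Range.** For N of 19 to 21 and mITT rates of about 20% to 50%, the understatement is about 1 to 3 percentage points with one undosed subject in the arm, and about 3 to 8 points with all three. Over the whole trial the three are 3/63 = 4.8% to 3/59 = 5.1% of those randomised.

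**Dosed subjects with no period-end ALP.** Protocol 8.2.3 fills such gaps by LOCF. SAP 3.3.4 allows no imputation beyond dates. Under SAP 5.2.5 these subjects stay in the denominator and cannot be in the numerator, so they are non-responders in effect, although no sentence says so. Under SAP 8 they would most naturally be noted as missing and left out of the percentage. SAP 7 does not record that LOCF was dropped.

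**The case against.** **A softer reading of SAP 5.2.5.** SAP 4.1 analyses mITT subjects by randomised group, so the sentence could mean mITT subjects grouped as randomised. SAP 8 ties table headers to the analysis population, which would leave undosed subjects out. This reading is possible, but the sentence refers to the number randomised and does not mention mITT. That both readings can be defended is itself a reason to settle the wording.

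**Low consequence.** The endpoints are untested and the primary MMRM in SAP 5.2.2 does not use this denominator. Sampling error is far larger: at 40% and n = 20 the 95% half-width is about 1.96 x sqrt(0.40 x 0.60 / 20) = 21 points, and one subject is 5 points. This stands and limits the weight of the point.

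**Dividing by all randomised is a recognised conservative convention.** It is, but the plan does not state it as a choice or reconcile it with SAP 4.1.

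**Stronger readings that a reader might infer.**
- *That Period 2 columns are also distorted.* SAP 1.1 says "subjects who were previously randomized to 500 mg or 1000 mg BID in Period 1 will continue to receive the same dose", which might suggest that continuing arms keep their Period 1 denominator while placebo switchers get a fresh one. The documents do not support this firmly. The visit windows in SAP 3.3.6 refer to randomisation to Period 2 without separating arms, the schedule in SAP 1.2 marks randomisation at Week 6 for everyone, and SAP 5 defines groups by regimen.
- *That the three are probably split unevenly over the arms.* Their arms and strata are not reported. Treating them as independent draws ignores the stratified, blocked scheme in SAP 3.2, and whether they belong to the 17 later subjects is not stated.
- *That the SAP calls them treatment failures.* No sentence does; it follows only from the arithmetic of the denominator. Likewise SAP 1.1 says that dosing had not yet begun. Never dosed is the natural inference after an enrolment stop, but it is not stated.

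**Conclusion.** The inconsistency is real and involves actual subjects. Read literally, SAP 5.2.5 multiplies an arm's Period 1 mITT responder rate by 0.95, 0.90 or 0.85 with one, two or three undosed subjects in an arm of about 20. Arms would be distorted relative to one another mainly if the split is uneven, which the documents do not let a reader judge.

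The conclusion assumes that the three were never dosed and that SAP 5.2.5 means what it says. It is confined to descriptive ALP responder proportions at the end of Period 1. It does not touch the primary analysis and does not establish a bias between continuing and switching groups in Period 2. It should be corrected because the correction is nearly free, but it does not threaten the trial's main result.

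**What to change.** 1. **SAP 5.2.5, ALP responder endpoints, Period 1:** set the denominator to *the number of mITT subjects in each treatment group, as randomized*.
2. **Periods 2 and 3:** state that the denominator is the mITT subjects who entered that period in that group. This also removes the ambiguity over who counts as randomised to Period 2.
3. **SAP 8:** align the general percentage rule, or state that SAP 5.2.5 overrides it for these endpoints.
4. **Missing period-end ALP:** say openly that such mITT subjects stay in the denominator as non-responders. This keeps the present effect of SAP 5.2.5 for them. Reconcile it with SAP 3.3.4 and list it in SAP 7 as a departure from the protocol's LOCF.
5. **Disposition (SAP 5.1):** show the three undosed subjects by arm. The section now plans to report population counts in aggregate.

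**Cost.** A few sentences and no new data. Denominators become slightly smaller, and any subject dosed but never assessed also leaves them. The by-arm disposition table should therefore show those subjects as well.

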1.2. SCHEDULE OF EVENTS

	Screening	Baseline	Initial Dosing Period			Dose-controlled Extension			Randomized Withdrawal			Follow-up
Visit Day	-28 to -1	0	Week 2	Week 4	Week 6	Week 8	Week 10	Week 12	Week 14	Week 16	Week 18	Week 22
Procedures												
Clinic visits	X	X			X			X			X	
Informed consent	X											
Eligibility criteria	X	X										
Demographics	X											
G6PD	X											
IgG4	X											
Urine drug test	X											
HIV/Hepatitis B, C	X											
Medical History	X	X										
Concomitant meds	X	X		X			X			X	X	
Physical examination	X	X		X			X			X		
Height/Weight/Vitals	X	X		X			X			X		
ECG	X	X		X			X			X		
Pregnancy testing	X	X								X		
Partial Mayo Score *	X	X		X			X			X		
CBC, CMP**, Lipids	X	X	X	X	X	X	X	X	X	X	X	
INR	X	X			X			X			X	

	Screening	Baseline	Initial Dosing Period			Dose-controlled Extension			Randomized Withdrawal			Follow-up
Visit Day	-28 to -1	0	Week 2	Week 4	Week 6	Week 8	Week 10	Week 12	Week 14	Week 16	Week 18	Week 22
Mayo Risk Score		X										
C-reactive protein *		X			X			X			X	
Fecal calprotectin *		X			X			X			X	
Randomization		X			X			X				
Dosing		X	X	X	X	X	X	X	X	X	X	
Adverse event monitoring		X	X	X	X	X	X	X	X	X	X	X
Telephone contact			X	X		X	X		X	X		X
Discharge											X	

* IBD subset only

** Including GGT

1.3. GLOSSARY OF ABBREVIATIONS

AE	Adverse Event
ALP	Alkaline Phosphatase
ALT	Alanine Aminotransferase
ANCOVA	Analysis of Covariance
AST	Aspartate Aminotransferase
BID	twice daily
BMI	Body Mass Index
CRF	case report form
CRP	C-reactive Protein
CSR	clinical study report
CTCAE	Common Terminology Criteria for Adverse Events
DSMB	Data and Safety Monitoring Board
ET	Early Termination
FAS	full analysis set
FC	Fecal Calprotectin
GGT	Gamma-Glutamyl Transferase
IBD	Inflammatory Bowel Disease
ITT	Intent-to-treat population
IxRS	interactive web/voice response system
LOCF	Last Observation Carried Forward
MedDRA	Medical Dictionary for Regulatory Activities
mITT	Modified intent-to-treat population
MMRM	Mixed Model with Repeated Measures
PP	per protocol
PSC	Primary Sclerosing Cholangitis
PT	Preferred Term
SAE	serious adverse event
SD	standard deviation
SOC	System Organ Classification
TEAE	treatment emergent adverse events
UDCA	ursodeoxycholic acid
WHO	World Health Organization

2. **OBJECTIVES**

Primary Objective:

The primary objective of this proof-of-concept study is to evaluate the effects of HTD1801 on serum alkaline phosphatase (ALP) levels in adult subjects with PSC.

Secondary Objective:

The secondary objectives of this study are to evaluate:

- the effects on concurrent disease activity of IBD, and
- the safety (inclusive of adverse events, serology, and vital signs) and
- the tolerability of HTD1801 over 18 weeks in adult subjects with PSC.

3. **GENERAL STATISTICAL CONSIDERATIONS**

